14.9.2. Physical Examination, Vital Signs, and Growth

Adverse changes from baseline in physical examination findings will be classified as AEs and analyzed accordingly.

Vital signs will be summarized descriptively at baseline and postbaseline time points and for changes from baseline by treatment group.

Height, weight, and head circumference (the latter only for patients ≤ 3 years of age) will be summarized descriptively at baseline and postbaseline time points and for changes from baseline by treatment group.

By-patient data listings will be provided.

14.9.3. Clinical Laboratory Tests

Changes in clinical chemistry, hematology, and urinalysis results from baseline to postbaseline study time points will be summarized descriptively. Shift tables over time will be presented for all central laboratory values, where applicable, using normal, low, or high based on normal range values. Listings of patients with abnormal results will be provided.

14.9.4. Electrocardiograms

By-patient data listings of ECG parameters will be provided. Changes from baseline in ECG intervals (PR, RR, QT, and QTcF) will be provided. QT interval will be corrected for heart rate using Fridericia's formula (QTcF).

14.9.5. Immunogenicity

Incidence and titers for ADAs to ALXN1210 will be summarized in tabular format.

14.10. Pharmacokinetic/Pharmacodynamic Analyses

Individual serum concentration data for all patients who receive at least 1 dose of ALXN1210 and who have evaluable PK data will be used to derive PK parameters for ALXN1210.

Graphs of mean serum concentration-time profiles will be constructed. Graphs of serum concentration-time profiles for individual patients may also be provided. Actual dose administration and sampling times will be used for all calculations. Descriptive statistics will be calculated for serum concentration data at each sampling time, as appropriate. Assessment of population-PK may be considered using data from this study or in combination with data from other studies.

Pharmacodynamic analyses will be performed for all patients who receive at least 1 dose of ALXN1210 and who have evaluable PD data.

Descriptive statistics will be presented for all ALXN1210 PD endpoints at each sampling time (Section 7.3). The PD effects of ALXN1210 administered IV will be evaluated by assessing the absolute values and changes and percentage changes from baseline in total and free C5 serum concentrations and change from baseline in cRBC hemolysis over time, as appropriate. Assessments of ALXN1210 PK/PD relationships may be explored using data from this study or in combination with data from other studies. Analyses will be conducted separately for naïve and previously eculizumab-treated patients.

14.11. Other Statistical Issues

14.11.1. Missing or Invalid Data

If a Day 1 assessment is missing, the Screening assessment will be used as the baseline assessment.

Missing data for QoL instruments will be handled as specified in the instrument instructions.

15. INFORMED CONSENT, ETHICAL REVIEW, AND REGULATORY CONSIDERATIONS

15.1. Informed Consent

The Investigator or designee is responsible for ensuring that the patient/caregiver understands the potential risks and benefits of participating in the study, including answering any questions the patient may have throughout the study and sharing in a timely manner any new information that may be relevant to the patient's willingness to continue his or her participation in the study.

The ICF will be used to explain the potential risks and benefits of study participation to the patient in simple terms before the patient is entered into the study, and to document that the patient is satisfied with his or her understanding of the risks and benefits of participating in the study and desires to participate in the study.

The Investigator or designee is responsible for ensuring that informed consent is given by each patient or the patient's legal representative. This includes obtaining the appropriate signatures and dates on the ICF prior to the performance of any protocol procedures and prior to the administration of investigational product. The Investigator or designee must retain the original version of the signed ICF. If the ICF is amended, the original signed, amended version must also be retained. A copy of the signed ICF(s) must be given to the patient.

As used in this protocol, the term "informed consent" includes all informed consent given by patients or, as applicable, informed assent by their legal representatives.

15.2. Data Monitoring Committee

An independent DMC comprising expert personnel in relevant biomedical fields who have no direct relationship with the study will be appointed by the Sponsor. The DMC will review and evaluate the accumulated study data for patient safety and make recommendations on continuing study drug administration or termination of the study. The DMC will review study information on a regular basis as outlined in the DMC charter, which is maintained separately from the study protocol.

Final decisions regarding the conduct of the study will be made by the Sponsor after consultation with the DMC. All appropriate regulatory authorities and IRBs/IECs will be notified of any significant action.

Each member of the DMC will be required to sign a contract agreement, which includes a confidentiality and financial disclosure statement, assuring no conflicts of interest as a condition for membership on the committee.

The specific responsibilities of the DMC are described in the DMC Charter, which is maintained as a separate document.

15.3. Ethical Review

All ICFs must be compliant with the ICH guideline on GCPs. Documentation of IRB/IEC approval of the protocol and the ICF must be provided to the Sponsor before the study may begin at the investigational sites.

15.4. Regulatory Considerations

This study will be conducted in accordance with:

- Consensus ethics principles derived from international ethics guidelines, including the Declaration of Helsinki and Council for International Organizations of Medical Sciences (CIOMS) International Ethical Guidelines
- The ICH GCP Guideline [E6]
- The ICH Clinical Trials of Medicinal Products in the Pediatric Population [E11]
- Applicable national and local laws and regulations

The Investigator or designee will promptly submit the protocol to applicable IRB/IEC(s).

Some of the obligations of the Sponsor will be assigned to third-party organization(s).

An identification code assigned to each patient by the EDC system will be used in lieu of the patient's name to protect the patient's identity when reporting AEs and other study-related data.

15.4.1. Changes/Deviations to Protocol

The Investigator may need to deviate from the protocol to eliminate an immediate hazard to a trial subject without prior notification of the IRB/IEC. Any deviations from the protocol must be fully documented. The deviation and the reasons for it should be submitted to the IRB/IEC, Sponsor, and appropriate regulatory authority if required (ICH GCP E6 [R1] 4.5.4).

After the commencement of the clinical trial, the Sponsor may make changes to the protocol. If those changes are significant, the regulatory authority and applicable IRB/IEC will be notified.

15.5. Publication Policy

The full terms regarding publication of the results of this study are outlined in the applicable Clinical Study Agreement.

17. APPENDICES

APPENDIX A. BLOOD SAMPLING VOLUMES

The following procedures for blood collection should be adhered to:

- 1. Number of attempts: The number of attempts for sampling blood is limited to 3 times per day. This means that, after 3 punctures for collection of blood have been performed and no or insufficient blood could be collected, no other puncture will be done on the same day.
- 2. Volume of blood samples: Per study patient, the study-related blood loss (including any losses in the collection procedure) should not exceed 3% of the total blood volume during a period of 4 weeks, and should not exceed 1% at any single time. The total volume of blood is estimated at 80 to 90 mL/kg body weight. Three percent (3%) is 2.4 mL blood per kg of body weight. If an investigator decides to deviate from these limits, the deviation must be fully documented, and the investigator should provide justification for the deviation. If the required blood volume cannot be obtained, due to the above mentioned safety limits, priority will be given to safety-relevant investigations.
- 3. EMLA (eutectic mixture of local anesthetics) cream/plaster: To minimize the possible pain and discomfort due to collection of blood, the Investigator should apply an EMLA cream/plaster at the puncture site.

Reference: European Commission. European Commission Ethical Considerations for Clinical Trials on Medicinal Products Conducted with the Paediatric Population: Recommendations of the ad hoc group for the development of implementing guidelines for Directive 2001/20/EC relating to the good clinical practice in the conduct of clinical trials on medicinal products for human use. 2008.

APPENDIX B. MANAGEMENT OF POTENTIAL DRUG INFUSION REACTIONS

Infusion of other monoclonal antibodies has been associated with infusion reactions, with onset typically during or shortly after completion of the infusion. For this reason, patients will be carefully observed during each infusion.

Patients who develop AEs of rash, hives, itching, or dysphagia of mild to moderate intensity during their infusion of ALXN1210 may continue to receive the infusion if deemed to be medically appropriate by the Investigator. Medical intervention may include, but is not limited to, slowing of the infusion rate (with or without treatment) or interrupting or stopping the infusion.

Any acute reaction should be treated according to standard medical practice depending upon clinical signs and symptoms. If a patient requires medical intervention, the patient should remain at the investigational site until his or her condition stabilizes. The AE and any associated concomitant medications must be captured on the patient's source document and electronic case report form (eCRF).

Some patients treated with IV infusions of monoclonal antibodies have experienced concurrent reactions with signs or symptoms that can be classified as acute allergic reactions/hypersensitivity reactions or cytokine release syndrome. Signs and symptoms include headache, fever, facial flushing, pruritus, myalgia, nausea, chest tightness, dyspnea, vomiting, erythema, abdominal discomfort, diaphoresis, shivers, hypertension, lightheadedness, hypotension, palpitations, and somnolence. Anaphylaxis might occur at any time during an infusion; therefore, patients will be monitored closely during the infusion. In addition, the re-administration of some monoclonal antibodies has been associated with serum sickness-like reactions manifesting 1 to 14 days after drug administration. All AEs that may indicate an infusion-related response will be graded according to the CTCAE v4.03 or higher.

Before any infusion is started, the treating physician and other appropriate personnel must make certain that medication (ie, adrenaline, inhaled beta agonists, antihistamines, corticosteroids) and other equipment to treat anaphylaxis are readily available. The infusion must be stopped immediately if Grade ≥ 2 allergic/hypersensitivity reactions (including drug fever) or Grade ≥ 3 cytokine release syndrome/acute infusion reaction occurs. The Sponsor must be notified within 24 hours of any infusion reaction requiring interruption or discontinuation of study drug.

Patients who experience a reaction during the administration of study drug should be treated according to institutional guidelines. For a Grade 1 or Grade 2 infusion reaction, the infusion should be temporarily stopped and treatment with an antihistamine (eg, diphenhydramine 25 to 50 mg orally or equivalent) and acetaminophen (650 mg orally or equivalent) may be considered. If the patient's signs and symptoms have resolved (with or without administration of the above medication), the infusion may be restarted. However, the patients should be infused at a slower rate and be monitored closely for any signs and symptoms of infusion reactions during the remainder of the infusion. Patients experiencing an infusion reaction should be observed in the clinic until resolution of the reaction, or until the Investigator determines the patient is no longer at risk. Patients who experience a severe reaction during administration of study drug resulting in discontinuation of study drug should undergo all scheduled safety, PK, and PD evaluations required by the protocol.

If anaphylaxis occurs according to the criteria listed below, then administration of subcutaneous epinephrine (1/1000, 0.3 mL to 0.5 mL, or equivalent) should be considered. In the case of bronchospasm, treatment with an inhaled beta agonist also should be considered. Patients administered an antihistamine for the treatment or prevention of an infusion reaction should be given appropriate warnings about drowsiness and impairment of driving ability before being discharged from the center.

Clinical Criteria for Diagnosing Anaphylaxis:

Anaphylaxis is highly likely when any 1 of the following 3 criteria is fulfilled:

- Acute onset of an illness (minutes to several hours) with involvement of the skin, mucosal tissue, or both (eg, generalized hives, pruritus or flushing, swollen lips-tongue-uvula), and at least 1 of the following:
 - Respiratory compromise (eg., dyspnea, wheeze-bronchospasm, stridor, reduced PEF, hypoxemia)
 - Reduced BP or associated symptoms of end-organ dysfunction (eg, hypotonia [collapse], syncope, incontinence)
- Two or more of the following that occur rapidly after exposure to a likely allergen for that patient (minutes to several hours):
 - Involvement of the skin-mucosal tissue (eg, generalized hives, itch-flush, swollen lips/tongue/uvula)
 - Respiratory compromise (eg., dyspnea, wheeze/bronchospasm, stridor, reduced PEF, hypoxemia)
 - Reduced BP or associated symptoms (eg, hypotonia [collapse], syncope, incontinence)
 - Persistent gastrointestinal symptoms (eg, crampy abdominal pain, vomiting)
- Reduced BP after exposure to known allergen for that patient (minutes to several hours):
 - Systolic BP of less than 90 mm Hg or greater than 30% decrease from that person's baseline

Source: Sampson, 2006

Abbreviations: BP = blood pressure; PEF = peak expiratory flow

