11.7.2. Severity Assessment

The severity of AEs will be graded using Common Terminology Criteria for Adverse Events (CTCAE) version 4.03 or higher. A grading (severity) scale is provided for each AE term. Each CTCAE term is a Lowest Level Term (LLT) per the Medical Dictionary for Regulatory Activities (MedDRA®). Each LLT will be coded to a MedDRA preferred term (PT).

Grade refers to the severity of the AE. The CTCAE assigns a grade of 1 through 5, with unique clinical descriptions of severity for each AE (Table 7).

Table 7:	Adverse	Event Severity	Grading Scale
----------	---------	----------------	----------------------

Grade	Description
Grade 1	Mild; asymptomatic or mild symptoms; clinical or diagnostic observations only; intervention not indicated
Grade 2	Moderate; minimal, local or noninvasive intervention indicated; limiting age-appropriate instrumental ADL ^a
Grade 3	Severe or medically significant, but not immediately life-threatening; hospitalization or prolongation of hospitalization indicated; disabling; limiting self-care ADL ^b
Grade 4	Life-threatening consequences; urgent intervention indicated.
Grade 5	Death related to AE.

Abbreviations: ADL = activities of daily living; AE = adverse event

Any change in the severity of an AE should be documented based on specific guidelines in the eCRF Completion Guidelines.

Severity and seriousness must be differentiated: severity describes the intensity of an AE, while the term seriousness refers to an AE that has met specific criteria for an SAE as described in Section 11.7.4.

^a Instrumental ADL refers to preparing meals, shopping for groceries or clothes, using the telephone, managing money, etc.

^b Self-care ADL refers to bathing, dressing and undressing, feeding self, using the toilet, taking medications, and not bedridden.

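### Appendix B lets the Investigator continue an infusion through moderate allergic signs, although its own stop rule for Grade 2 allergic reactions is mandatory

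*Protocol*

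**What the plan says.** Three instructions stand in Protocol Appendix B.

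- **Permission.** Patients who develop "rash, hives, itching, or dysphagia of mild to moderate intensity during their infusion of ALXN1210 may continue to receive the infusion", provided the Investigator considers this medically appropriate. The next sentence gives possible interventions, among them "slowing of the infusion rate (with or without treatment) or interrupting or stopping the infusion". None of these is mandatory.
- **Mandatory stop.** "The infusion must be stopped immediately if Grade ≥ 2 allergic/hypersensitivity reactions (including drug fever". The same sentence extends the immediate stop to cytokine release syndrome or an acute infusion reaction, but only from Grade 3.
- **Advised pause.** "For a Grade 1 or Grade 2 infusion reaction, the infusion should be temporarily stopped". The infusion may be restarted at a slower rate once signs and symptoms have resolved.

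On grading, the appendix says: "All AEs that may indicate an infusion-related response will be graded according to the CTCAE v4.03 or higher". Table 7 in Protocol Section 11.7.2 labels Grade 1 as mild and describes Grade 2 as "Moderate; minimal, local or noninvasive intervention indicated".

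On reporting, the appendix says: "The Sponsor must be notified within 24 hours of any infusion reaction requiring interruption or discontinuation of study drug". SAP Section 7.3.1 counts the patients with an infusion interruption and the infusions interrupted, from Day 1 to Day 183.

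**The concern.** The permission is written by symptom and intensity. The stop rules are written by type of reaction and CTCAE grade. The appendix does not say how the two fit together. A child with moderate hives during an infusion can fall under both, and the appendix then allows the infusion to continue in one paragraph and requires it to stop in another.

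What is at stake is mainly conduct at the bedside. Two sites facing the same moderate allergic reaction could act differently, each pointing to Appendix B. Protocol Section 9.10 relies on the same appendix, with the home health care manual, for infusions given at home. Reporting follows the choice: a reaction managed by slowing the rate prompts no 24-hour notice and is not an interruption in the SAP 7.3.1 summary. The adverse event itself is recorded either way.

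**Working it through.** The plan gives no figure to reproduce here, so the check sets the instructions side by side.

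**Step 1: do the grades overlap?** The permission covers mild to moderate events. Infusion-related events are graded by CTCAE, and Table 7 labels Grade 1 mild and Grade 2 moderate. On that scale the permission covers Grades 1 and 2. The mandatory stop for allergic reactions starts at Grade 2, and the advised pause covers Grades 1 and 2. The ranges overlap.

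**Step 2: do the events overlap?** The permission sits in the appendix on infusion reactions and concerns events arising during the infusion. Of signs that can be classified as allergic or hypersensitivity reactions or cytokine release syndrome, the appendix says: "Signs and symptoms include headache, fever, facial flushing, pruritus", and the list continues. Itching is therefore named. Generalized hives and pruritus appear again in the anaphylaxis criteria. Overlap is natural for hives and itching. It is weakest for isolated dysphagia, which Protocol Section 10.3 also lists as a PNH symptom.

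**Step 3: compare the required action.**

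| Named sign during infusion | Permission | Stop rules | Result |
|---|---|---|---|
| Grade 1, classed as infusion reaction | may continue | should pause | may against should |
| Grade 2, classed as allergic or hypersensitivity | may continue | must stop at once | may against must: conflict |
| Grade 2, classed as infusion reaction but not allergic | may continue | should pause (the mandatory stop starts at Grade 3) | may against should |
| Grade 1 or 2, classed as neither | may continue | none applies | no conflict |

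**Step 4: is there a rule of precedence?** No text ranks the paragraphs, makes the permission subject to the stop rules, or exempts the four named signs from them.

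**Step 5: what changes in the data?** For the second row, a site that stops owes the 24-hour notice and adds one patient and one infusion to the SAP 7.3.1 counts. A site that slows the rate and continues does neither. One patient is 1/13 = 7.7% of planned enrolment, or 1/12 = 8.3% of the 12 patients on whom the report described in the SAP is based. The documents give no rate for such reactions, so this is the effect per event and not a forecast.

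**The case against.** The strongest reply is that nothing here is contradictory. The permission is a conditional may, it depends on medical judgement, and its own list of interventions includes interrupting or stopping. A site that stops satisfies every sentence, and on an ordinary reading a specific must overrides a general may. Much of this stands. A reader might infer that Appendix B gives opposite orders that no site can follow, and the documents do not support that. The reply does not remove the problem, because the permission expressly reaches moderate intensity and names hives and itching. An Investigator who relies on it for a moderate allergic reaction is using words that the appendix supplies, and must infer the limit unaided.

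A second reply concerns grading. Section 11.7.2 says that CTCAE describes severity separately for each term, so moderate itching need not equal a Grade 2 allergic reaction. This is fair for individual cases. Table 7 is nevertheless the only scale in the documents that defines moderate, and the overlap exists whenever the event is graded 2 and judged allergic.

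Third, being on the list of signs does not make a sign allergic, and skin signs alone do not meet the anaphylaxis criterion that also asks for respiratory compromise or reduced blood pressure. This stands too. A reader might infer that all four signs always fall under the stop rules, but moderate dysphagia due to PNH, for example, does not.

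Finally, the consequences for reporting are limited. Serious events go to the Sponsor within 24 hours under Section 11.7.6 whether or not the infusion was interrupted.

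**Conclusion.** The inconsistency is real and narrow. For moderate (Grade 2) signs judged to be allergic or hypersensitivity reactions, Appendix B permits continuing what it elsewhere says must be stopped, and it states no precedence. At Grade 1, and for Grade 2 infusion reactions that are not allergic, the tension is only between may and should. Events that are neither kind of reaction are not in conflict.

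The conclusion rests on two assumptions: that moderate means Grade 2, as Table 7 labels it, and that the sign is classed as allergic, which is natural for hives and itching and doubtful for isolated dysphagia.

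The size is one descriptive count and one non-serious notification per affected patient. A reader might infer that efficacy or PK/PD results are at risk; nothing in the documents supports this, and no primary or secondary endpoint is affected. The reason to act is the safety of children under infusion and uniform conduct across sites.

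**What to change.** Make two insertions in Appendix B at the next amendment.

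1. In the permission, after the condition on the Investigator's judgement, add: *unless the event is a Grade ≥ 2 allergic/hypersensitivity reaction or a Grade ≥ 2 infusion reaction, in which case the stopping rules below apply*.
2. In the sentence advising a temporary stop for Grade 1 or 2 infusion reactions, add: *(for Grade 1 rash, hives, itching or dysphagia, the Investigator may instead continue as described above)*.

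The first makes the permission subject to the stop rules and leaves it intact for moderate events that are neither allergic nor infusion reactions. Limiting the whole permission to Grade 1 would be simpler but would remove it for those events without need. The second settles the milder tension at Grade 1 in favour of the existing discretion, for the four named signs only.

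Check the home health care manual for the same text, and send sites a short notice.

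The cost is two clauses, that check and the notice, with no added visit, procedure or patient. The one loss is the Investigator's discretion to continue through a moderate infusion reaction that is not allergic, which the appendix already advises against.

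### Protocol Appendix B gives conflicting instructions for mild to moderate rash, hives or itching during an infusion

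*Protocol*

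**What the plan says.** The second paragraph of Protocol Appendix B covers events that arise while the drug is running: patients with rash, hives, dysphagia or itching "of mild to moderate intensity during their infusion of ALXN1210 may continue to receive the infusion if deemed to be medically appropriate by the Investigator". It then lists what can be done: "Medical intervention may include, but is not limited to, slowing of the infusion rate (with or without treatment) or interrupting or stopping the infusion". All of these are options.

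The fourth paragraph describes reactions seen with monoclonal antibodies that can be classed as allergic/hypersensitivity or as cytokine release syndrome. "Signs and symptoms include headache, fever, facial flushing, pruritus" and others. It adds: "All AEs that may indicate an infusion-related response will be graded according to the CTCAE v4.03 or higher".

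The fifth paragraph sets a mandatory rule: "The infusion must be stopped immediately if Grade ≥ 2 allergic/hypersensitivity reactions" occur. The same sentence applies the rule to cytokine release syndrome or acute infusion reaction from Grade 3 upward. The next sentence sets a reporting duty: "The Sponsor must be notified within 24 hours of any infusion reaction requiring interruption or discontinuation of study drug".

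The sixth paragraph deals with reactions during administration: "For a Grade 1 or Grade 2 infusion reaction, the infusion should be temporarily stopped". The infusion may be restarted, at a slower rate, once signs and symptoms have resolved.

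Section 9.5 sends sites to Appendix B to identify and manage infusion reactions. Section 9.10 does the same for home infusions and also names a home health care manual.

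**The concern.** The second paragraph is worded by intensity, and the fifth and sixth by CTCAE grade. Under the protocol's own Table 7 the two vocabularies cover the same range, and the appendix does not say how they relate. Two overlaps follow:

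- **(a)** A moderate rash, hives or itching event judged allergic falls under a discretionary permission to continue and also under a mandatory immediate stop.
- **(b)** A Grade 1 or 2 event handled as an infusion reaction falls under the same permission and also under an instruction to pause.

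In overlap (a), an Investigator who relies on the written permission breaches a written requirement, in a study of children. The choice also affects reporting. The 24-hour notice to the Sponsor depends on whether the reaction required interruption or discontinuation, so two sites handling the same event could differ on whether notice is due. At home the infusion is given away from the site, and Appendix B is one of only two sources named for managing a reaction there.

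**Working it through.** No arithmetic in the plan bears on this point, so the check is a comparison of the texts.

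**Inputs**

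- Permission to continue, mild to moderate rash, hives or itching: Appendix B, second paragraph.
- Mandatory immediate stop, allergic/hypersensitivity reaction of Grade 2 or higher: Appendix B, fifth paragraph.
- Temporary stop, infusion reaction of Grade 1 or 2: Appendix B, sixth paragraph.
- Grade 1 described as mild and Grade 2 as moderate: Section 11.7.2, Table 7.

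**Step 1: do the rules use a common scale?** Appendix B has every AE that may indicate an infusion-related response graded by CTCAE. With Table 7, mild to moderate then reads as Grades 1 to 2. That overlaps the mandatory stop at Grade 2 and the temporary stop at both grades.

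**Step 2: can the named symptoms belong to the classes in the stop rules?** The fourth paragraph lists pruritus among signs that can be classed as allergic/hypersensitivity or cytokine release syndrome. The anaphylaxis criteria name hives and pruritus, though only together with another feature. Dysphagia is left out of overlap (a): Appendix B does not tie it to allergy, and Section 10.3 lists it as a sign of PNH.

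**Step 3: count the instructions for rash, hives or itching.**

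| Class and grade | Second paragraph | Fifth or sixth paragraph | Instructions |
|---|---|---|---|
| Infusion reaction, Grade 1 | may continue | should pause | 2, differing |
| Infusion reaction, Grade 2 | may continue | should pause | 2, differing |
| Allergic reaction, Grade 1 | may continue | none (mandatory stop starts at Grade 2) | 1 |
| Allergic reaction, Grade 2 | may continue | must stop at once | 2, differing |

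Combinations with differing instructions: 1 + 1 + 0 + 1 = 3 of 4. If an allergic reaction also counts as an infusion reaction, the Grade 1 allergic row gains the instruction to pause, and the count is 4 of 4. Of the 3, one sets the permission against a must and two set it against a should.

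**Step 4: is there a tie-break?** No sentence in Appendix B, Section 9.5 or Section 9.10 separates the events that each rule covers or gives an order of precedence. The home health care manual is not among the documents, so whether it settles the point is unknown.

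**The case against.** The strongest reply is that the paragraphs can be read together. The second paragraph orders nothing, and interrupting or stopping are among its options. A patient who is paused and then restarted more slowly complies with every paragraph. On this reading the mandatory stop simply limits the permission and needs no precedence sentence. The appendix also defers to standard medical practice and institutional guidelines, and Section 9.5 describes it as guidance.

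This stands in part. Stopping never breaches the second paragraph, so the conflict arises only when the permission is used. But the pause satisfies both rules only because the permission to continue is then left unused. The second paragraph mentions no pause and offers slowing the rate as an alternative to interrupting.

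A second reply is that a moderate symptom is not automatically a Grade 2 allergic reaction, because CTCAE describes severity separately for each term (Section 11.7.2). This is a real limit. The documents do not give the term-level grading, so the extent of overlap (a) is uncertain. It bears less on overlap (b), where the temporary stop covers both Grade 1 and Grade 2.

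A third reply is that the count depends on how the grid is drawn and weighs a should like a must. The separate tally of the two kinds answers the second part. The count describes the wording and does not measure harm. Leaving cytokine release syndrome out of the grid does not change the result, because its mandatory stop starts at Grade 3, above the mild to moderate range.

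Finally, AE recording and SAE reporting (Section 11.7.6) and permanent discontinuation for serious infusion reactions (Section 8.3.1) do not depend on this ambiguity. That is correct and limits the consequences to conduct during the infusion and to the 24-hour notice.

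**Conclusion.** The inconsistency is real and stands in the current text of Appendix B. On Table 7's general scale, 3 of 4 grade-by-class combinations for rash, hives or itching carry differing instructions, or 4 of 4 if allergic reactions also count as infusion reactions. The Grade 2 allergic combination matters most, because there the permission meets a mandatory stop. The two infusion-reaction combinations are weaker, since they set the permission against an advisory instruction.

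The conclusion assumes that mild and moderate mean Grades 1 and 2, as Table 7 describes them. Confidence is medium, because term-level grading could narrow the overlap and the home health care manual has not been seen. The documents give no event rate, so no number of affected patients can be stated. The point should be fixed, but it does not touch the validity of the planned analyses.

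**What to change.** The second, fifth and sixth paragraphs of Appendix B must be reconciled into one statement of action by grade. It should say how a symptom-level AE, an allergic/hypersensitivity reaction and an infusion reaction are told apart, use CTCAE grade throughout, and state which instruction governs when more than one applies. The events that trigger the 24-hour notice should follow from that statement. The sponsor's clinical lead decides the content; nothing here favours one clinical rule over another. The home health care manual named in Section 9.10 should be checked against the result.

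The cost is a wording clarification in one appendix and a consistency check of one manual. Sample size, endpoints and planned analyses do not change.
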